4. STUDY POPULATION

4.1. Inclusion Criteria

Subjects must satisfy all of the following criteria to be included in the study:

1. Male or female pediatric subjects between birth (defined as 38 weeks gestational age) and less than 18 years of age at the time of consent.
2. Pediatric subjects with the presence of documented VTE confirmed by appropriate diagnostic imaging and requiring anticoagulant therapy for at least 90 days (list of VTE provided in Section [7.1](#)).
-Subjects <6 months old (Cohort 5) with the presence of documented VTE confirmed by appropriate diagnostic imaging and requiring anticoagulant therapy for at least 6 to 12 weeks.
3. Subjects must have received at least 5 days of heparin (LMWH or SP Xa inhibitors or UFH according to the edoxaban label for VTE treatment) therapy prior to randomization to treat the newly identified index VTE. In addition, prior to being randomized to edoxaban or SOC, subjects initially treated with VKA are recommended to have an INR ≤ 2.5 .
4. Subject and/or parent(s)/legal guardian(s) or legally acceptable representative is informed and provides signed consent for the child to participate in the study with edoxaban treatment. Pediatric subjects with appropriate intellectual maturity will be required to sign an assent form in addition to the signed informed consent from the parent(s)/legal guardian(s) or any legally acceptable representative.
5. Female subjects who have menarche must test negative for pregnancy at Screening and must consent to avoid becoming pregnant by using an approved contraception method throughout the study Appendix [17.3](#).

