4.2. Exclusion Criteria

Subjects who meet any of the following criteria will be disqualified from entering the study:

1. Subjects with active bleeding or high risk of bleeding contraindicating treatment with LMWH, SP Xa inhibitors, VKAs, or direct oral anticoagulants (DOACs; identified high risk of bleeding during prior experimental administration of DOACs).
2. Subjects who have been or are being treated with thrombolytic agents, thrombectomy or insertion of a caval filter for the newly identified index VTE.
3. Administration of antiplatelet therapy is contraindicated in both arms except for low dose aspirin defined as 1-5 mg/kg/day with maximum of 100 mg/day (see Appendix [17.4.1](#)).
4. Administration of rifampin is prohibited during the study and subjects on concomitant use of rifampin are excluded.
5. a) Subjects with severe hepatic impairment or hepatic disease associated with coagulopathy (eg, acute hepatitis, chronic active hepatitis, and cirrhosis).

- b) Subjects with ALT $>5 \times$ the upper limit of normal (ULN) or total bilirubin $>2 \times$ ULN with direct bilirubin $>20\%$ of the total at Screening.
- c) Subjects with aPTT >50 seconds or international normalized ratio [INR] >2.0 not related to anticoagulation therapy).
- 6. Subjects with estimated glomerular filtration rate (eGFR) $<30\%$ of normal for age and size (see Appendix 17.7).
- 7. Subjects with stage 2 hypertension defined as blood pressure (BP) systolic and/or diastolic confirmed $>99^{\text{th}}$ percentile + 5 mmHg (see Appendix 17.8).
- 8. Subject with thrombocytopenia $<50 \times 10^9/\text{L}$ at Screening Visit. Subjects with a history of heparin-induced thrombocytopenia may be enrolled in the study at the Investigator's discretion.
- 9. Life expectancy less than the expected study treatment duration (3 months).
- 10. Subjects who are known to be pregnant or breastfeeding.
- 11. Subjects with any condition that, as judged by the Investigator, would place the subject at increased risk of harm if he/she participated in the study including contraindicated medications identified in Appendix 17.4.
- 12. Subjects who participated in another interventional clinical study or were treated with an experimental therapy with less than a 30 day wash-out period prior to identifying the qualifying index VTE.
- 13. Hypersensitivity to the active ingredient or to any of the excipients of any components of the trial treatment.

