4.3. Additional Requirements

4.3.1. Stopping Rules for Age-based cohort during PK/PD assessment:

- In each age cohort if the estimated edoxaban median AUC based on the observed PK data in the approximately 12 subjects (between 5 and 12 subjects in Cohort 5) on Day 5 PK assessment is 50% higher or 50% lower than the median AUC from the simulated patient population profiles, dose reevaluations for Phase 3 subjects will be recommended to achieve the exposure comparable to adult 60 mg doses. The enrollment of subjects in the corresponding age cohort will be put on hold until reevaluation of the dose for this age cohort.

4.3.2. Stopping Rules for Study:

An IDMC may recommend termination of the study. Termination may be made for any of the following reasons:

- Concern about significantly higher bleeding risk relative to one of the study arms,
- Concern about drug-induced liver injury,
- Any other safety concern based on benefit/risk evaluation.

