5.6.3. Reasons for Discontinuation of Study Treatment

Subjects may **discontinue the treatment** for any of the following reasons

1. End of requirement for anticoagulant therapy
2. Reasons related to adverse events (AEs):
 - Initiating or continuing study drug places the subject at undue hazard as determined by the Investigator;
 - Serious adverse event (SAE) or other safety concern that is related to study drug treatment as determined by the Investigator;
 - Major bleeding event as determined by the Investigator;
 - Aggravation or new occurrence of renal insufficiency with eGFR $\leq 30\%$ of normal for age and size;
 - Hepatic test abnormalities as follows:
 - Elevation of ALT and/or AST $\geq 3 \times$ ULN and TBL $\geq 2 \times$ ULN simultaneously.
 - ALT and/or AST $\geq 8 \times$ ULN requires an immediate interruption of study drug treatment and prompt repeat testing to confirm abnormality.
 - Clinical jaundice requires an immediate interruption of study drug treatment and prompt repeat testing to confirm abnormality;
 - Any elevation of transaminases combined with clinical symptoms of liver injury;
 - If a subject discontinues study drug due to confirmed liver enzyme abnormalities or jaundice, the subject will have additional evaluations at the discretion of the Investigator as follows:
 - Hepatitis A, B, C, and E screening (anti-HAV IgM, HBsAg, anti-HCV plus viral titer, and evaluation for Hepatitis E);
 - Abdominal ultrasound;
 - Antinuclear antibody (ANA) and anti-SmAb;
 - Cytomegalovirus (CMV);
 - Epstein-Barr virus (EBV);

- Additional evaluations as deemed appropriate by the Investigator to exclude other causes of liver enzyme and bilirubin elevations.

Subject's follow-up will be required on a weekly basis until the values (transaminases and total bilirubin) return to baseline or clinically acceptable levels in the judgment of the Investigator. For the above laboratory blood tests, using the central laboratory is recommended. However, if circumstances warrant the use of a local laboratory, copies of the local laboratory results will be required. All clinically significant hepatic enzyme abnormalities and/or hepatic events are to be documented in the eCRF and prompt submission of the adjudication dossier should also occur for events that led to study drug discontinuation or were reported as SAEs.

3. Unplanned cardiac surgery due to aggravation of cardiac conditions;
4. Pregnancy;
5. Study terminated by Sponsor;
6. Protocol violation;

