 - Height and body weight (may be performed by an Investigator or other healthcare provider designated by the Investigator).
- Assess the subject for active bleeding, high risk for bleeding and any other contraindications for treatment with LMWH, or UFH, SP anti-FXa, VKAs or NOACs.
- INR assessment and aPTT measurement to monitor coagulation for all subjects
- Ensure that the subject qualifies with regard to the following laboratory tests for exclusion criteria:
 - Liver function assessments (ALT, AST, TBL, ALP)
 - Serum chemistry panel, Serum creatinine, and eGFR
 - Hematology
 - Urinalysis
 - Urine pregnancy test (for post-menarchal females)
- Samples taken as part of routine care outside study auspices may be analyzed by local laboratories and the results used to qualify the subject provided the tests (INR, aPTT, ALT, TBL, eGFR and platelets) were performed for the newly diagnosed index VTE before randomization. Alternatively, the central laboratory may be used for the above study qualification laboratory tests. If central laboratory is also used at the same visit with a resulting discrepancy for exclusion criteria, the local laboratory result will still be used to qualify the subject.
- Review concomitant medications for assessment of exclusion criteria.
- Assess for and record AEs and concomitant medications.

Full documentation for the above qualifying procedures and related results are required even if local laboratory results were used to qualify the subject.

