11.4.3.3. Clinical Laboratory Evaluation Analyses

Descriptive statistics will be provided for the clinical laboratory results by scheduled time of evaluation and by treatment arm for the Safety Analysis Set, as well as for the change from baseline. The baseline value is defined as the last non-missing value before the initial administration of study drug. In addition, mean change from baseline will be presented by treatment arm for the maximum and minimum post-treatment values and the values at the Discontinuation Visit.

Shift tables (in categories of low, normal, and high) will be provided for each treatment arm for selected clinical laboratory parameters. Also, the number and percentage of subjects with clinically relevant abnormal clinical laboratory values while on study drug will be calculated for each treatment arm for selected clinical laboratory parameters. All abnormal clinical laboratory values will be presented in a listing. Specifically, the number and percentage of subjects with elevation of liver enzymes (ALT, AST) and TBL, according to various multiples of ULN will be summarized by treatment arm. The number and percentage of subjects with concurrent elevation of ALT or AST $\geq 3 \times$ ULN and TBL $\geq 2 \times$ ULN will also be summarized by treatment arm.

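### Entry limits admit subjects who already meet hepatic interruption or potential Hy's Law criteria, and the liver table does not separate baseline from new elevations

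*Combined protocol and SAP*

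**What the plan says.** **Entry.** Section 4.1 enrols "Male or female pediatric subjects between birth (defined as 38 weeks gestational age) and less than 18 years of age". Exclusion 5b in section 4.2 removes subjects with ALT above 5 x ULN. It removes those with total bilirubin (TBL) above 2 x ULN only if they also have "direct bilirubin $>20\%$ of the total at Screening". AST is among the screening tests in section 6.1, but no exclusion limits it. Exclusion 5a covers "Subjects with severe hepatic impairment or hepatic disease associated with coagulopathy" and gives no laboratory threshold.

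**On treatment.** Section 5.6.3 lists a combined elevation (ALT and/or AST at least 3 x ULN with TBL at least 2 x ULN) among the reasons for which a subject may discontinue. Two items in the same list are mandatory. One is ALT and/or AST of at least 8 x ULN. The other reads: "Clinical jaundice requires an immediate interruption of study drug treatment and prompt repeat testing to confirm abnormality".

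**Reporting and counting.** Section 9.3.1 has every case meeting the combined laboratory criterion reported within 24 hours as a potential Hy's Law case, regardless of causality. Section 11.4.3.3 tabulates by arm "The number and percentage of subjects with concurrent elevation of ALT or AST" of at least 3 x ULN with TBL of at least 2 x ULN, and sets no condition on the baseline value. Section 4.3.2 names "Concern about drug-induced liver injury" as a ground on which the IDMC may recommend termination.

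**The concern.** The entry limits and the on-treatment limits use different analytes, different multiples of ULN and a different bilirubin definition. Where they overlap, a subject can be correctly enrolled and already satisfy a rule that interrupts drug.

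The hepatic items in 5.6.3 do not say that the abnormality must be new or worse. The renal item in the same list is confined to worsening or newly arising insufficiency, so the protocol makes that distinction for the kidney and not for the liver.

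Two things are at stake. The first is on-treatment exposure. Under 11.4.3.1, a bleed counts as on-treatment only while the subject is on drug or within 3 days of an interruption. The second is the liver safety count. An abnormality that preceded the first dose and one that arose on drug would sit in the same cell of the 11.4.3.3 table. Few such cases are expected, so each one carries weight.

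**Working it through.** The plan states no figure to reproduce here, so the check is a comparison of thresholds. Values are multiples of ULN; D is direct bilirubin as a share of the total.

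1. Excluded (4.2, 5b): ALT > 5, or (TBL > 2 and D > 0.20). AST is unrestricted.
2. Combined criterion (5.6.3, 9.3.1, 11.4.3.3): (ALT ≥ 3 or AST ≥ 3) and TBL ≥ 2.
3. Transaminase interruption (5.6.3): ALT ≥ 8 or AST ≥ 8.
4. Jaundice interruption (5.6.3): any clinical jaundice.

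Subjects who pass rule 1 and meet rule 2 have ALT ≤ 5, with ALT ≥ 3 or AST ≥ 3, and either TBL exactly 2, or TBL > 2 with D ≤ 0.20. Subjects who pass rule 1 and meet rule 3 have AST ≥ 8 with ALT ≤ 5, and bilirubin that does not trigger 5b.

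Applying the rules to specific profiles:

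| ALT | AST | TBL | D | Eligible under 5b | Combined criterion | ≥ 8 x ULN rule |
|---|---|---|---|---|---|---|
| 4 | 4 | 3 | 10% | yes | met | no |
| 3 | 1 | 2 | 50% | yes | met | no |
| 1 | 3 | 2.5 | 20% | yes | met | no |
| 1 | 9 | 1 | 10% | yes | no | met |
| 1 | 1 | 4 | 10% | yes | no | no |
| 4 | 4 | 3 | 30% | no | met | no |
| 6 | 6 | 1 | 10% | no | no | no |

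The fifth profile meets no laboratory rule, but meets rule 4 if the bilirubin is visible as jaundice. The last two are controls that 5b does exclude.

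**Timing.** In Table 17.1 the liver panel is scheduled at screening and next at Month 1. The Day 5 chemistry entry is footnoted to renal function. Without unscheduled testing, a laboratory abnormality must persist to Month 1 to be seen again. Only visible jaundice, or a screening value the investigator already knows, could act at the start of dosing.

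**Whether other analyses separate the cases.** The shift tables in 11.4.3.3 use low, normal and high, so they cannot show whether a subject was already above 3 x or 2 x ULN. Change from baseline is summarised as a mean by arm.

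**Size.** One subject in an arm of 137 is 1/137 = 0.7%; two are 2/137 = 1.5%.

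**The case against.** Several points on the other side are sound.

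- The hepatic items in 5.6.3 sit under reasons related to adverse events. Section 9.1 sends out-of-range values known before consent to medical history, and 11.4.3.2 requires a treatment-emergent event to be new or worse. A stable abnormality known at entry is thus arguably not an adverse-event reason. This stands for adverse-event tables. It does not reach the two mandatory interruption sentences, the Hy's Law report or the laboratory count.
- The combined criterion is permissive, and section 5.3 asks for interrupted drug to be resumed as soon as circumstances permit. This stands: the mandatory items are interruptions, not permanent stops.
- Investigator judgement (exclusion 11) and exclusion 5a may keep some of these children out. Neither sets a laboratory limit, so the gap stays open.
- Reporting regardless of causality is deliberately broad. Section 9.3.1 adds a causality assessment and a narrative, and abnormalities leading to interruption or discontinuation go to blinded adjudication. These safeguards help interpretation but do not remove a baseline-positive subject from the table.
- Section 11.7 defers definitions to a SAP, which could supply a baseline rule. The text available here contains none.

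A reader might infer more: that on-treatment time is generally lost from Day 1, that the primary result is biased, or that pre-existing abnormalities could by themselves end the study. The documents do not support these readings. The Month 1 schedule limits the first. On the second, subjects who stop drug are followed to Month 3 (5.6.1), the primary analysis is mITT by randomized arm (11.4.1.1), and randomization is stratified by age. On the third, termination rests on IDMC judgement, not a raw count.

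**Conclusion.** The inconsistency holds on the protocol's own thresholds: an eligible subject can meet a hepatic interruption rule or the potential Hy's Law laboratory criterion before the first dose. The consequence is limited. It affects on-treatment exposure in the subjects concerned and the interpretability of the concurrent-elevation count in 11.4.3.3; the effect on the primary mITT analysis is minor.

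The documents do not say how many subjects would be affected. That the number is small, and that newborns with indirect jaundice are the likeliest group, are assumptions; the protocol gives no liver-test data by age or thrombosis site. The count is affected only if the combined elevation is still present at a post-baseline test. The point merits correction because single potential Hy's Law cases matter in a liver review and the repair is cheap.

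**What to change.** 1. The sponsor should reconcile exclusion 5b in section 4.2 (and its copy in the synopsis) with the hepatic items in 5.6.3 and the reporting rule in 9.3.1, so that sites know how an abnormality present at entry is handled. Which clinical limits apply is the sponsor's decision.
2. In 11.4.3.3, tabulate concurrent ALT/AST and TBL elevations by arm separately for subjects who did and did not meet the criterion at baseline, and list the baseline-positive subjects by arm. Use the baseline definition already in that section, the last non-missing value before first dose.

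The cost is amendment wording, one baseline flag and slightly smaller denominators in that table. No new sampling is needed, because ALT, AST and TBL are already collected at screening.

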5.6.4. Reasons for Withdrawal at any Time During the Study

Withdrawal of a subject will only occur by definition if no additional protocol scheduled visits or Follow-Up Visit is possible. The withdrawal definition is mostly appropriate for those cases that occur in the Main Treatment Period because of the requirement to continue subjects on scheduled visits even if they discontinue treatment prior to Month 3 (Visit 5). If a subject withdraws after Month 3 this would be classified as a discontinuation from treatment and study.

The cases appropriate for withdrawal during the Main Treatment Period are:

- Withdrawal of subject consent by subject or legal guardian(s)
- Death
- Lost to follow-up (attempts should be made to not have any subject lost to follow-up)
- AE that occurs during the Main Treatment Period that requires withdrawal.

5.6.5. Discontinuation Procedures

In accordance with the Declaration of Helsinki and other applicable regulations, a subject has the right to discontinue study treatment or withdraw consent for participation in the study at any time and for any reason without prejudice to his or her future medical care by the physician or at the institution.

While subjects are encouraged to complete all study evaluations, they may discontinue study treatment or withdraw from the study at any time and for any reason without penalty. Every effort will be made to determine why any subject discontinues study treatment or withdraws from the study prematurely. This information should be recorded.

The most likely reasons for withdrawal are death, lost to follow-up or withdrawal of consent, or an AE in which case all subsequent visits will NOT be possible as stated in the protocol.

All subjects who classify as discontinued from the study treatment with an ongoing AE must be followed until the event is resolved or deemed stable even if they are not willing to participate in the study any longer. If a subject discontinues study treatment or withdraws after dosing, all data normally collected prior to study discharge should be collected at the time of discontinuation from study treatment or withdrawal, and at the scheduled visit of the study.

In case of withdrawal, a genuine effort must be made to determine the reason(s) why a subject fails to return for the necessary visits. If the subject is unreachable by telephone, a registered letter, at the minimum, should be sent to the subject requesting him/her to contact the study center.

If a subject is withdrawn or discontinued from study treatment, the IXRS will be called by the study center to register the subject status.

Please see suggested classification of discontinuation and withdrawal status in [Table 5.2](#).

Table 5.2: Classification of Discontinuation and Withdrawal Status for Subjects by Scheduled Visit

	Discontinue Treatment	Discontinue Study	Withdrawal
Randomization through Month 3	Eligible	Not Eligible (Need to follow through Month 3 with Follow-Up Visit)	Eligible (Assumes no additional visit is possible)
Beyond Month 3 through Month 12	Eligible	Eligible (A discontinuation study visit will be conducted with Follow-Up Visit)	Not Eligible (Unless no discontinuation visit is possible)

5.6.6. Follow-up Procedures

A 30-day follow-up for safety assessment will be scheduled after the Month 3 visit for all subjects participating in the 3-month Main Treatment Period (for Cohort 5, the intended duration of treatment is 6-12 weeks).

Subjects who extend toward 12 months of study treatment and decide to no longer participate will have a subsequent 30-day Follow-Up Visit after their discontinuation visit during the extension period.

A 30-day Follow-Up Visit may be performed with a phone call if the following conditions have NOT occurred:

- An SAE was not experienced by the subject at the last visit or during the interval of time from the last visit to the Follow-Up Visit,
- An event (recurrent VTE, or bleeds) was not experienced by the subject at the last visit or during the interval of time from the last visit to the Follow-Up Visit.

5.6.6.1. Temporary Interruption of Study Drug

If a subject's treatment with study drug must be interrupted for medical or surgical reasons (eg, hospital admission for an invasive procedure, a major medical condition, surgery, thrombocytopenia due to cytotoxic medication, or dental work); use of a prohibited concomitant medication; or other reasons (eg, temporary situation that prevents subject adherence with the study drug administration schedule, etc.), the subject's study drug should be resumed as early as the situation allows. Edoxaban should be discontinued for 24 hours prior to the initiation of the procedures (depending on PK/PD data in children). Subjects should be encouraged to restart study drug after an interruption except when absolutely contraindicated. The duration of study drug interruption can vary depending upon the individual circumstances, and study drug may be resumed regardless of the duration of time that it had been interrupted. Any subject who temporarily interrupts study drug for more than 3 days will have the reason recorded in the eCRF.

5.6.6.2. Subject Re-Screening Procedures

Re-screening (retesting of laboratory test results) is permitted only once for any subject with Sponsor approval who failed to meet eligibility criteria upon initial screening related to a specific inclusion/exclusion criteria. If a subject needs to be re-screened for any time dependent module (ie, laboratory, vital signs, etc.), the Investigator will perform an unscheduled visit **within 30 days of the original Screening visit** and the appropriate module will be used to accommodate new data that would make the subject eligible to be randomized. The subject identification number will remain the same at the time of rescreening.

The initial screening information and the reason why the subject is ineligible for the initial evaluation will be uploaded into the EDC system. Re-screening of a subject may occur only once. If there is a failure to meet study entry criteria, the failed subject will be recorded in the Screening Log and EDC.

